4 STUDY DESIGN

4.1 General Description

This study is a multicenter, open-label extension study of LMTM in subjects with mild to moderate AD or bvFTD at the time they first enrolled in a double-blind trial.

Participation in this study will be offered to any subject who completed participation in a TauRx-sponsored Phase 2 or Phase 3 double-blind study, *i.e.*, Studies TRx-237-005, TRx-237-007, TRx-237-008, or TRx-237-015. Only AD subjects who have completed the full double-blind period of the originating studies (including the 1-month post-treatment follow-up), or bvFTD subjects who completed the full double-blind treatment period through Visit 9 in TRx-237-007, will be eligible for inclusion in this open-label extension study (see Section 6.2.1 for guidance regarding study drug dosing for bvFTD subjects entering this extension study).

Subjects may enter this study at the final designated visit in the double-blind study, provided subjects and caregivers have had sufficient time to consider the study prior to giving consent, or at any subsequent time. Subjects may continue participation at the same site at which they participated in the originating double-blind study or transfer to a geographically close investigational site (that also participated in the same study). Eligibility for continued open-label treatment is to be determined by the original investigator and, if applicable, a referral to a new site made. The new investigator will have access to the subject's prior study eCRFs and is to confirm eligibility (see Section 5); Baseline testing can be repeated as necessary in the judgment of the new investigator. The initial visit will be designated Visit 1.

The initial LMTM dose is 200 mg/day (one 100-mg tablet twice daily [*b.i.d.*]). The dose may be increased (at Visit 3 or at any subsequent dispensing visit as determined by the investigator during the treatment period) to a maximum of 300 mg/day (or in those countries where limited by a CA or EC, 200 mg/day) in response to benefit as judged by the investigator. Alternatively, the dose may be interrupted at any time (for up to 30 days on a given occasion) or decreased to a minimum of 100 mg/day (at any time at or after Visit 2) as needed in response to safety assessments (see Section 6.2.2). The recommended decrement or increment of dose adjustment is 100 mg/day. The study drug will be dispensed in 13-week (\pm 2-week) supplies.

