4.3 Duration

The study will continue until alternate options for access to treatment are available, *i.e.*, commercialization or, depending on country, on a Named Patient or compassionate basis, or availability *via* a Managed Access Program. (See Section 5.4 for a discussion of other reasons for study termination.)

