5.3 Discontinuation/Withdrawal

For a discussion of reasons for dose adjustment or permanent discontinuation of study medication on the basis of safety, see Section 6.2.3. These include clinically evident hemolytic anemia (Section 6.2.3.1), serotonin syndrome (Section 6.2.3.2), prolongation of the QT interval on ECG and decrease in renal function (Section 6.2.3.3).

Subjects may discontinue study drug and withdraw (drop out) from the study at any time for any reason. The caregiver may also withdraw his or her consent at any time for any reason. If a caregiver withdraws his or her consent, the subject must then also be withdrawn if alternative arrangements are not available (*e.g.*, an alternate caregiver). Furthermore, the investigator also has the right to discontinue trial medication if he or she judges that treatment is no longer appropriate, the subject's clinical condition is worsening, or for an adverse event.

At the completion of each 12-month period of open-label treatment, the principal investigator must determine whether or not continued treatment is warranted on the basis of continued benefit and safety and tolerability profile. If eligible, the subject and/or caregiver must give informed consent for continued participation. In Germany and the Netherlands, continuation of treatment is not permitted if the subject is unable to give consent.

If study drug is discontinued or the subject/caregiver elect(s) not to re-enroll in a subsequent open-label treatment phase, the reason should be recorded as one of the following:

- AE
- Death
- Lack of efficacy (including progressive disease or worsening of cognitive capacity; in Germany, this includes loss of the ability to give consent if the legal representative or caregiver is not available or does not agree to continued participation)
- Lost to follow up
- Withdrawal by subject or legal representative (or caregiver), including specific reasons wherever possible
- Protocol deviation
- Non-compliance with study drug
- Pregnancy
- Study terminated by Sponsor
- Physician decision, including specific reason(s) wherever possible

- Other (specify)

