9.6.1 Adverse Events

Adverse events will be coded to System Organ Class and preferred term using the Medical Dictionary for Regulatory Activities (MedDRA) version adopted at the start of the double-blind study in which the subject previously participated (Version 15.0 or later).

Adverse events will be regarded as treatment-emergent (TEAE) if they start on or after the first dose of study drug administration in the open-label study or if they were present prior to the first date of study drug administration and increased in severity or relationship to study drug while on study treatment. Those that resolved prior to the first dose or were ongoing at the same intensity and relationship will be regarded as pre-treatment AEs and not summarized.

Tabular summaries are described below, with the number and percentage of subjects reporting each type of event presented. If a subject reports the same preferred term more than once, it is counted only once within that category. Further, for a given tabulation, the preferred term will only be counted once in its worst severity, greatest relationship to treatment, and worst action taken.

Pre-study AEs, those present at the time of the first dose of study drug administration, will be presented separately.

An overall summary table of TEAEs will be produced showing the number and percent of subjects with the following: TEAE, severe intensity TEAE, TEAE related to study drug, AESIs, serious TEAE, TEAE with outcome of death, and TEAE leading to interruption, dose reduction, or discontinuation from the study. In addition, the summary table will include the number of TEAEs, severe TEAEs, TEAEs related to study drug, and serious TEAEs.

Separate summaries of incidences (number and percentage of subjects) of all individual TEAEs and the subsets of drug-related TEAEs, TEAEs that are severe in intensity, serious TEAEs, and TEAEs leading to change in dose will be provided.

The subset of TEAEs that have an onset more than 7 days after the last dose of study drug will be considered post-treatment. An overall summary table of the number and percent of subjects with post-treatment AEs will be prepared.

All AEs will be presented in a data listing. In addition, listings also will be provided for SAEs, AEs leading to death, AEs leading to discontinuation of study drug, AEs leading to dose reduction and/or interruption, and any other AEs that are of special interest (to be defined prior to database lock).

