This analysis will be repeated for subjects who returned an adequate amount of packages to allow for a meaningful calculation.

The frequency and percentage of subjects in the following duration of exposure categories (based on total duration of exposure, inclusive of interruptions) will be presented according to target visit windows defined in Appendix A.

The cumulative number and percentage of subjects across the categories will also be summarized, as well as total subject years of exposure, defined as the sum of exposure in years, will also be presented.

All study drug administration and compliance data will be presented in listings, including chronological dates of administration, number of tablets dispensed and returned with corresponding package ID, treatment duration, mean and modal daily dose, compliance, and any associated comments.

An additional listing will provide a chronological record of study drug administration including the first dose and any subsequent dose increases, reductions, or interruptions, and any associated comments.

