## **7. SAFETY ANALYSES**

### **7.1 Adverse Events**

There are two CRFs contributing adverse event data.

- **Prior Study – Adverse Events CRF:** All adverse events as recorded during prior studies 005, 007 and 015 will be automatically uploaded to the Prior Study – Adverse Events CRF and adverse events recorded during the 008 study will be recopied from the 008 records by the site to the Prior Study – Adverse Events CRF. The only field that can be modified by the site is the OLEX end date as applicable. Additionally there is a comment field where text can be entered by site.
- **Adverse Event CRF:** New adverse events or changes to an existing adverse event will be recorded on the Adverse Event CRF.

Adverse events will be coded to SOC and PT using MedDRA (version 16.0). The coding process is described in the Data Management Plan.

AEs are grouped as follows and source(s) of data identified:

1. **Prior AEs:** AEs that were ongoing at the end of the prior study but that resolved before Day 1 of dosing in 020 or that started and resolved during the gap between studies. The source would be both the Prior Study – Adverse Events CRF and the (020) Adverse Event CRF.
2. **Pre-existing AEs:** AEs that were ongoing on Day 1 of dosing in 020 - source is the Prior Study – Adverse Events CRF. The source would be both the Prior Study – Adverse Events CRF and the (020) Adverse Event CRF.

3. Study-emergent AEs: AEs that started on or after Day 1 of dosing in 020, excluding post-treatment AEs (defined in #5 below). The source would be the (020) Adverse Event CRF.
4. All AEs: Whether pre-existing or study-emergent (merge of AEs that were ongoing on Day 1 of dosing) excluding post-treatment AEs. Sources are the Prior Study – Adverse Events CRF and the (020) Adverse Event CRF (note, this is a merge of #2 and 3 above *only*).
5. Post-treatment AEs: The study-emergent AEs (3# above) that have an onset more than 14 days after the last dose of study drug or that worsen in intensity or treatment attribution following discontinuation more than 14 days after the last dose of study drug.

The tabular summaries will be provided for AEs, with the number and percentage of subjects reporting each type of event. If a subject reports the same preferred term more than once, it is counted only once within that category. Further, for a given tabulation, the preferred term will only be counted once at its worst severity and strongest relationship to treatment.

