After missing date imputation, if the end date and start date of two or more AEs with the same Preferred Term are less than or equal to two days apart, then the AE will be considered to be the same event and will be counted as one event. If the end date is missing for the first AE or the start date for the sequential AE is before the end date for the first AE, then the AEs will be considered one event and will be counted once. In every other case, the events will be counted separately.

The following summaries will be provided for AE categories 2-4 above:

- An overall summary of AEs summarizing the number and percent of subjects, and the number of unique AEs, in the following categories: any AE, severe AE, AE related to study drug, serious AE, related serious AE (serious adverse reaction or SAR), AE with outcome of death, adverse events of special interest (AESIs), AE leading to dose reduction, AE leading to dose interruption, AE leading to withdrawal of study drug, and AE leading to dose reduction, dose interruption, or withdrawal of study drug.
- Number of subjects who experienced AEs and total number of unique AEs by MedDRA SOC and PT.
- Number of subjects who experienced AEs by MedDRA SOC, PT, and worst severity.

- Number of subjects who experienced AEs by MedDRA SOC, PT, and strongest relationship to study drug (Related/Not Related). Events reported as “Possibly Related,” or “Related” will be included in the Related category. Events reported as “Unlikely Related” or “Not Related” will be included in the Not Related category. At each level of subject summarization a subject is classified according to the strongest relationship, as determined by the investigator, if the subject reported one or more events. AEs with a missing relationship will be considered related for this summary.
- Number of subjects who experienced serious AEs (SAEs) and total number of unique serious AEs by MedDRA SOC and PT (and subsets for fatal and nonfatal SAEs as well as related SAEs (SARs), as described above).
- Number of subjects who experienced severe AEs and total number of unique severe AEs by MedDRA SOC and PT. AEs with missing severity will be considered severe for inclusion in this summary.
- Number of subjects who experienced AEs leading to change in dose and total number of unique AEs leading to change in dose (dose reduction, dose interruption, and study drug withdrawal, separately and combined) by MedDRA SOC and PT.

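### Adverse event tables carry no exposure adjustment although follow-up is open-ended and unequal, so columns cannot be compared if time on drug differs; the prior-treatment tables are the weakest

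*SAP*

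**What the plan says.** **The AE measure.** Protocol 9.6.1 and SAP 7.1 agree on subjects and percentages. The protocol has "Tabular summaries are described below, with the number and percentage of subjects reporting each type of event presented", and the SAP has "The tabular summaries will be provided for AEs, with the number and percentage of subjects reporting each type of event". The overall table adds event counts: "An overall summary of AEs summarizing the number and percent of subjects, and the number of unique AEs, in the following categories". In SAP Appendix G the AE layouts carry only an N in each column header. None has a person-time denominator, an interval split or a time-to-event summary. SAP 5.2 does split discontinuations by time period.

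**Which events.** SAP 7.1 says "The following summaries will be provided for AE categories 2-4 above". These categories are pre-existing AEs, study-emergent AEs, and the two merged.

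**Follow-up.** Protocol 4.3: "The study will continue until alternate options for access to treatment are available". Under Protocol 4.1 a subject may enter at the final double-blind visit, given enough time to consider "prior to giving consent, or at any subsequent time". Re-consent is needed about every 12 months. Protocol 5.3 adds a country-dependent stop: "In Germany and the Netherlands, continuation of treatment is not permitted if the subject is unable to give consent". The periods in SAP 5.2 run from Day 1 to beyond Day 683.

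**Person-time.** SAP 6 says "total subject years of exposure, defined as the sum of exposure in years, will also be presented". This figure appears only in Tables 14.3.1.1 (AD, bvFTD, All Subjects) and 14.3.1.2 (non-users of AChEI/memantine).

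**The concern.** A percentage of subjects with an event depends on how long they were watched as well as on risk. Where everyone has the same planned follow-up, that dependence is often tolerable. Here follow-up has no planned length, and subjects can leave at any yearly re-consent. The SAP nevertheless sets AD beside bvFTD, sets six prior-treatment groups beside each other, and repeats the AE tables for non-users of AChEI/memantine.

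Unequal time in this study across the prior-treatment columns is plausible. Protocol section 2 ties prior dose to source study: for example, 200 mg/day was the active dose in studies 005 (AD) and 007 (bvFTD). Protocol 4.2 gives source-study lengths of 19 months (005), 16 months (015), 12 months (007) and 2 months (008), which affects when subjects could enter.

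One of the two primary objectives is long-term safety and tolerability. In an uncontrolled extension the AE rates are the main usable output on that objective, so they should be readable across the columns the SAP chooses to print.

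**Working it through.** The plan states no AE rate, sample size or power to reproduce (Protocol 9.2 is not applicable). Every rate below is an assumption, used only to show how the planned statistic behaves.

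**1. Which columns have person-time**

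| AE columns | Subject-years planned? | AE category |
|---|---|---|
| AD, bvFTD, All | Yes, Table 14.3.1.1 | 2, 3 and 4, separate tables |
| Non-users of AChEI/memantine | Yes, Table 14.3.1.2 | 2, 3 and 4, separate tables |
| Prior treatment: AD 8/150/200/250 mg, bvFTD 8/200 mg | No | 4 only (pre-existing plus study-emergent) |

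The last row covers Tables 14.3.2.1.3.3, 14.3.2.2.3.3 and 14.3.2.10.3.3 to 14.3.2.13.3.3. To adjust them, a reader would have to join Listing 16.2.5.2 (exposure by subject) to Listing 16.2.1.1.1 (prior treatment).

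**2. Equal risk, unequal follow-up.** With a constant first-event rate r per year and follow-up of T years, crude % = 100 × (1 − exp(−rT)). The ratio of 2 years to 1 year is (1 − exp(−2r)) / (1 − exp(−r)) = 1 + exp(−r).

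| Assumed rate per 100 subject-years | Crude % at 1 y | Crude % at 2 y | Ratio |
|---|---|---|---|
| 2 | 2.0 | 3.9 | 1.98 |
| 5 | 4.9 | 9.5 | 1.95 |
| 10 | 9.5 | 18.1 | 1.90 |
| 30 | 25.9 | 45.1 | 1.74 |
| 100 | 63.2 | 86.5 | 1.37 |

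The exposure-adjusted rate is the same at both times in every row.

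**3. Same cut-off, different dropout.** With event rate h, other dropout rate g and cut-off T, crude % = 100 × h/(h+g) × (1 − exp(−(h+g)T)), and mean time at risk = (1 − exp(−(h+g)T))/(h+g). Take h = 0.1 per year and T = 2 years.
- g = 0.2: 15.0% over a mean of 1.50 years.
- g = 0.8: 9.3% over a mean of 0.93 years.

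Both are 10.0 per 100 subject-years, yet the crude percentages differ by 15.0/9.3 = 1.6.

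**4. Events that end treatment.** Use the same formulas with g = 0.2 and T = 1.5 years.
- h = 0.5: 46.4% over a mean of 0.93 years.
- h = 0.1: 12.1% over a mean of 1.21 years.

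The shorter-exposed column now has the higher percentage. The crude ratio, 46.4/12.1 = 3.8, understates the true rate ratio of 5.

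**5. Does a single rate cure it?** Assume a front-loaded hazard of 0.6 per year for 3 months, then 0.05 per year. The rate is subjects with an event divided by time to first event or end of follow-up.

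| Follow-up | Crude % | Mean years at risk | Per 100 subject-years |
|---|---|---|---|
| 0.5 y | 15.0 | 0.446 | 33.6 |
| 1 y | 17.1 | 0.866 | 19.7 |
| 2 y | 21.1 | 1.674 | 12.6 |

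The crude percentage rises with follow-up while the rate falls. One rate alone can therefore flatter the longer-followed column, and an interval split is needed beside it.

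**The case against.** The strongest case against acting has four parts.

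- **The study is descriptive.** Protocol 9.3.2 plans no inferential statistics. That stands, and any interval added should be labelled descriptive. It does not make a descriptive percentage comparable across columns with different exposure.
- **Subgroup work is deferred.** The Version 3.0 change log says AE subgroup analyses move to the Integrated Summary of Safety, which considers a subject's whole exposure. This is partial mitigation only, because the SAP still plans subgroup AE tables of its own.
- **The reader can do the division.** Event counts and subject-years are both planned for AD, bvFTD, All and non-users, so a crude event rate can be formed. It would be wrong to say that percentages are all the SAP offers. The counts are still unadjusted as printed, they do not give a first-event rate, and the route is closed for the prior-treatment columns.
- **Rates can mislead too.** Step 5 shows this, and early onset is plausible because some subjects take LMTM for the first time here. A rate per subject-year also has no meaning for AEs already ongoing on Day 1. Both points stand and shape the fix.

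A reader might infer that columns with longer exposure will look less safe. The documents do not support that: exposure by column is not given, and step 4 shows the order can reverse when AEs cause early stopping.

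**Conclusion.** The gap is real: no AE table adjusts for exposure in a study whose follow-up is open-ended and unequal by design. Under equal true risk and a constant hazard, 2 years against 1 year inflates the crude percentage about 1.4 to 2.0 times, for assumed rates from 100 down to 2 per 100 subject-years. Whether any two columns differ by that much in exposure cannot be known from the documents, and neither can the direction.

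A reader might infer a larger distortion by setting half a year against three years. At 10 per 100 subject-years that gives 4.9% against 25.9%, about fivefold. Nothing in the documents supports column averages that far apart: the last named target visit in SAP Appendix A is Week 104, and the Day 1 to beyond Day 683 periods are category labels, not expected exposure.

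The prior-treatment tables are the part most worth repairing, since they lack matching exposure and mix events that arose before this study with those that arose in it. Adjusted rates would not by themselves make this study comparable with the double-blind trials, because only completers enter and many were already treated. This should be changed, as an inexpensive improvement to a descriptive safety report.

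**What to change.** 1. Keep all crude counts and percentages.
2. First reconcile the on-treatment window. SAP 7.1 calls AEs post-treatment when onset is more than 14 days after last dose; Protocol 9.6.1 uses more than 7 days.
3. For study-emergent AEs only (SAP category 3), add subjects with an event per 100 subject-years at risk. Censor time at first event or the end of the reconciled window, and give an exact Poisson 95% CI labelled descriptive. Apply this to the overall, SOC/PT, serious, fatal, AE-withdrawal and AESI tables.
4. In the six prior-treatment tables, show study-emergent AEs separately and add their rates.
5. Put total subject-years in every AE column header, including each prior-treatment group.
6. For the key categories, show incidence by the intervals already in SAP 5.2, because a single rate assumes a roughly constant hazard.

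First-dose, last-dose and AE onset dates are already collected, so no new data are needed. The cost is programming and length: SAP 6 derives total exposure only, so time at risk must be newly derived for each event term, and the tables become longer.

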A double-blind, placebo-controlled, Phase 2 study was also conducted (TRx-237-008), however, this study was terminated early for administrative reasons; 9 subjects were randomized. These subjects are also eligible for the open-label extension study.

The intent of this extension study is to provide LMTM treatment to those subjects in whom the benefit is judged to outweigh the risk, and to assess the longer-term safety and tolerability of LMTM given in doses of up to 300 mg/day, or in those countries where limited by a Competent Authority (CA) or Ethics Committee (EC), 200 mg/day. Treatment with LMTM in this study will either be *de novo* in subjects having been randomized to placebo or will be a continuation of treatment, albeit not necessarily at the same dose, to those subjects having been previously randomized to LMTM.

LMTM 150 mg/day is the lowest dose to which a subject participating in the Phase 2 or Phase 3 studies may be randomized. However, 200 mg/day has been chosen as the initial dose for continuation of treatment in this open-label extension study as it is intermediate to the doses previously used. This dose has been chosen because 250 mg/day was the active treatment in Study TRx-237-008 and is the active treatment for half of the subjects receiving LMTM in Study TRx-237-015, and 200 mg/day is the active treatment in Studies TRx-237-005 and TRx-237-007. Subjects previously randomized to placebo will receive LMTM for the first time at this dose. All subjects with AD will have undergone at least a 3-week period off-treatment prior to entry into this study; as prior treatment assignment will be blinded, this provides a standardized approach for treating all subjects. Dose interruptions are allowed at any time (to a maximum of 30 days on a given occasion) and dose adjustments are flexible to a minimum of 100 mg/day and a maximum of 300 mg/day (or 200 mg/day in those countries where limited by a CA or EC), to be based on safety and tolerability and benefit as judged by the investigator. As the acceptable risk/benefit balance will vary from subject to subject, the selection of dose is left to the discretion of the investigator, together with the subject and caregiver(s), based on judgment of the risk/benefit balance in any given subject.

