9.3.2 General Considerations

Results will be summarized descriptively; no inferential statistics are planned. Tabulations will be on the basis of all subjects pooled and also with subjects categorized separately by diagnosis and also by study of original participation. Data from the prior study will be mapped into the open-label database.

For purposes of calculations of change from baseline, Baseline (Visit 1) for the open-label study will be used. Depending on the parameter, the data may have been acquired during the double-blind study of prior participation.

For purposes of data tabulations, target visit windows will be assigned in the SAP.

Listings of by-subject data will be organized by subject number.

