## **4. GENERAL ANALYSIS CONSIDERATIONS**

The Safety population will include all subjects who take at least one dose of study drug. All analyses described in this SAP will be based on the Safety Population. All subjects entering the study, even if not known to have taken a dose, will be accounted for in a listing.

The statistical analyses will be reported using summary tables, figures, and data listings. Continuous variables will be summarized with means, standard deviations, medians, minimums, and maximums. Categorical variables will be summarized by counts and by percentage of subjects in corresponding categories.

For purposes of calculations of change from baseline, Baseline (Visit 1) for the open-label study will be used. Depending on the parameter, the data may have been acquired during the double-blind study of prior participation.

Summary tables will present results by diagnosis (AD or bvFTD) and an “All Subjects” column.

Individual subject data obtained from the CRFs (including mapped data), central clinical laboratory (local laboratory results are entered on the CRFs), and any derived data will be presented by subject in data listings. Listings will include relative study day, where negative values will indicate visits prior to first dose of study drug in 020, and any data collected after discontinuation of study drug will be flagged as follow-up. All data captured on the CRF, including specific descriptions of ‘other’ and comments fields, will be included on the listings. Listings will be sorted by subject number.

All analyses and tabulations will be performed using SAS® Version 9.4 or higher. Tables, listings, and figures will be presented in RTF format. Upon completion, all SAS® programs will be validated by an independent programmer. In addition, all program output will undergo a senior level statistical review. The validation process will be used to confirm that statistically valid methods have been implemented and that all data manipulations and calculations are accurate. Checks will be made to ensure accuracy, consistency with this plan, consistency within tables, and consistency between tables and corresponding data listings. Upon completion of validation and quality review procedures, all documentation will be collected and filed by the project statistician or designee.

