- Number of subjects who experienced unique protocol-specified AESIs and total number of unique protocol-specified AESIs by MedDRA SOC and PT.

The above summaries of AEs will also be presented for non-AChEI (acetylcholinesterase inhibitor)/Memantine users. Selected summaries of AEs will also be presented by diagnosis and prior study treatment. Depending on controlled study results, analyses of selected TauRx AE groupings may be undertaken.

A tabular summary of post-treatment adverse events (#5 above) by MedDRA SOC and PT will be provided.

The AE listing will include Prior AEs, All AEs, and Post-treatment AEs (#1, 4, and 5 above). Prior AEs, Pre-existing AEs and Post-treatment AEs will be flagged.

In addition, listings will also be provided for study-emergent or post-treatment SAEs (including subsets for fatal and non-fatal SAEs), study-emergent AEs leading to dose reduction, interruption or study drug withdrawal, and study-emergent or post-treatment AESIs. Post-treatment AEs will be flagged.

---

 Relationship is determined by the Investigator

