## 8. OTHER ASSESSMENTS

### 8.1 MMSE

For MMSE in subjects with AD, change from baseline for pooled treatment allocation will be analyzed using a restricted maximum likelihood based repeated measures linear mixed model. The model will include fixed effects for AChEI/Memantine use as randomized in the prior study (Yes and No), time since baseline in the prior study (continuous), AChEI/Memantine use as randomized in the prior study by time interaction and the prior study baseline MMSE, prior study (015 and 005) and region (The Americas and RoW). In addition, the baseline MMSE from the prior study will be included as a covariate. An unstructured covariance model will be used. The Kenward and Roger method of calculating the denominator degrees of freedom will be used for the tests of fixed effects. Annualized LS means will be provided. Additionally, observed means according to the visit windowing in [Appendix A](#) will be provided.

If more than 20 bvFTD subjects have MMSE values in 020, the above analysis will be repeated for bvFTD subjects.

If more than 10 subjects with AD discontinue AChEI/Memantine in 020, then summary of MMSE at the visits prior to and the visits subsequent to discontinuation will be provided.

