**Table 14.3.2.1.3.3**  
**Overall Summary of Adverse Events (Pre-existing Adverse Events and Study-emergent Adverse Events) by Diagnosis and Prior Study Treatment**  

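### The AE tables by prior treatment have one AD 8 mg/day column that appears to mix the control arms of Studies 005 and 015, so study differences can be read as prior-dose differences

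*SAP*

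**What the plan says.** SAP 7.1 plans the split in one sentence: "Selected summaries of AEs will also be presented by diagnosis and prior study treatment". Appendix F turns it into six tables: 14.3.2.1.3.3, 14.3.2.2.3.3, 14.3.2.10.3.3, 14.3.2.11.3.3, 14.3.2.12.3.3 and 14.3.2.13.3.3. The first is titled "Overall Summary of Adverse Events (Pre-existing Adverse Events and Study-emergent Adverse Events) by Diagnosis and Prior Study Treatment". All six merge AEs already present at the first 020 dose with those arising later. The Appendix G shells give AD columns of 8, 150, 200 and 250 mg/day and bvFTD columns of 8 and 200 mg/day. Cells are event counts, or subject counts with crude percentages. No column is split by originating study.

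Protocol Section 2 places the doses. It says that "200 mg/day is the active treatment in Studies TRx-237-005 and TRx-237-007" (005 is AD, 007 is bvFTD) and that "250 mg/day was the active treatment in Study TRx-237-008 and is the active treatment for half of the subjects receiving LMTM in Study TRx-237-015". Of Study 008 it says that "this study was terminated early for administrative reasons; 9 subjects were randomized". It describes 005, 015 and 007 as placebo-controlled and calls 150 mg/day the lowest randomised dose. It never mentions 8 mg/day, and the SAP uses that label without defining it.

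Protocol 9.3.2 states: "Tabulations will be on the basis of all subjects pooled and also with subjects categorized separately by diagnosis and also by study of original participation". SAP Section 4 keeps the split by diagnosis and an all-subjects column. No table in Appendix F is by originating study.

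**The concern.** These six tables are the only planned tables that set former control subjects, who meet a full dose for the first time in 020, beside subjects who were already on LMTM. Protocol Section 2 gives those new starters as the reason for the 2-week safety visit, and long-term safety is a primary objective. A reader will naturally scan across the columns for a dose pattern.

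Across the AD columns, however, originating study changes along with prior dose. The studies differ in length: protocol 4.2 gives 19 months for 005 and 16 for 015, with a 12-month treatment option for some 015 subjects. They may also differ in subjects, sites, time spent in 020 and AEs carried over. Any such difference enters the percentages, pushing 200 mg/day one way from the control column and 150 and 250 mg/day the other. That could create a dose pattern or hide one. The SAP's own MMSE model (8.1) includes prior study as a fixed effect, so the plan already treats originating study as relevant elsewhere.

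**Working it through.** The plan has no figure to reproduce: protocol 9.2 says that a sample size calculation does not apply, and neither document gives arm sizes or AE rates by study. The check is to trace the columns and then do mixture arithmetic.

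**Source of each AD column**

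| AD column | Source | Basis |
|---|---|---|
| 200 mg/day | 005 | Stated in protocol Section 2 |
| 250 mg/day | 015, plus at most 9 from 008 | Stated in protocol Section 2 |
| 150 mg/day | 015 | By elimination: the other half of its LMTM subjects |
| 8 mg/day | Controls of 005 and 015 (and any from 008) | By elimination: both studies have control arms, there is no placebo column, and no other AD column is left |

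Study 008 is a small part of the 250 mg/day column. If 100 subjects come from 015 (an assumption), 008 contributes at most 9/109 = 8.3%. If 250 do, it is at most 9/259 = 3.5%. It is ignored below.

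**Formulas with no effect of prior dose.** Let p5 and p15 be the AE percentages in subjects from 005 and 015, d = p5 - p15, and w the share of the 8 mg/day column that comes from 015.

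- 8 mg/day column: w x p15 + (1-w) x p5
- 200 minus 8: p5 - [w x p15 + (1-w) x p5] = w x d
- 150 or 250 minus 8: p15 - [w x p15 + (1-w) x p5] = -(1-w) x d
- 200 minus 150 or 250: d, whatever w is
- 150 minus 250: 0

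The larger of w and 1-w is at least 0.5, so at least one comparison with the 8 mg/day column always carries half of d or more.

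**Illustration.** Assume p5 = 40% and p15 = 30%, so d = 10 points. Neither value is in the documents.

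| w | 8 mg/day column | 200 minus 8 | 150 or 250 minus 8 | 200 minus 150 or 250 |
|---|---|---|---|---|
| 0.2 | 38% | +2 | -8 | +10 |
| 0.5 | 35% | +5 | -5 | +10 |
| 0.8 | 32% | +8 | -2 | +10 |

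Halving d halves every difference; reversing its sign reverses them all.

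**After nesting.** Within 005, 200 minus control is 40 - 40 = 0. Within 015, 150 or 250 minus control is 30 - 30 = 0. The comparison of 200 with 150 or 250 is still 10 points, because no single study contains both.

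**The case against.** The strongest reply is that no comparison is planned. Protocol 9.3.2 rules out inferential statistics, and the SAP names no reference column and no difference for these tables. The protocol's summary of changes for Version 3.0 says that AE subgroup analyses were moved to the Integrated Summary of Safety. Listing 16.2.1.1.1 shows each subject's prior study identifier and prior treatment, so a split could be produced on request. This stands as far as it goes: there is no error rate to protect. It does not remove the risk of misreading, because columns ordered by dose invite comparison.

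Three stronger readings are tempting, and the documents do not support them.

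- A reader might take 8 mg/day as the documented control dose. It is an inference: the protocol says placebo and gives 150 mg/day as the lowest randomised dose.
- A reader might infer that following protocol 9.3.2 would have prevented the problem, or that the SAP breached it silently. By-study columns alone would merge control and active subjects within each study and would not nest dose within study. Protocol Section 9 and SAP Section 9 both leave changes to be documented in the study report. The missing by-study tabulation is a separate point.
- A reader might put a size on d from the studies' lengths. Suppose 005 subjects have 9 months in 020 and 015 subjects 12, with AE percentages of 1 - exp(-h x t). An assumed hazard h of 0.1 per year gives d of 9.5% - 7.2% = 2.3 points; an assumed 1.0 gives 63.2% - 52.8% = 10.4 points. The documents give no hazards, randomisation dates or common cut-off. The formula also counts only new events, whereas these tables include pre-existing AEs, and four of the six cover only AEs leading to dose changes or withdrawal.

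The confounding is also not uniform. The 150 versus 250 comparison lies within 015 apart from the few 008 subjects, and both bvFTD columns come from 007.

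**Conclusion.** The concern holds as a layout weakness in six descriptive tables. On the by-elimination reading of the 8 mg/day label, each AD active column is set against a control that contains its own study's control diluted with the other study's. The distortion is w x d for 200 mg/day and (1-w) x d, with opposite sign, for 150 and 250 mg/day. The comparison of 200 with 150 or 250 carries all of d. The 150 versus 250 comparison and the bvFTD columns are essentially unaffected.

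The algebra assumes only that prior dose has no effect and that AE percentages differ between studies. The size and sign of d and the value of w cannot be found from the documents, so the point values above are illustrations and not estimates. The change is worth making before the tables are run because it is cheap and these are the only tables that display former controls separately.

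**What to change.** In the six shells, nest AD prior treatment within originating study: 005 (control, 200 mg/day) and 015 (control, 150 mg/day, 250 mg/day). Put the 008 subjects in their own column or a footnote, and leave bvFTD unchanged. Define the 8 mg/day label in the SAP and reconcile it with the protocol's description of placebo. Add footnotes saying that the columns show prior and not current dose, and that 200 versus 150 or 250 mg/day remains a between-study comparison even after nesting.

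Separately, either add the tabulations by study of original participation that protocol 9.3.2 plans or record in SAP Section 9 that they are dropped. Adding them does not replace the nesting.

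The cost is SAP wording, one or two more columns in six shells, and smaller control denominators. No new data are needed: SAP 3.2 and Listing 16.2.1.1.1 already carry prior study identifiers and prior treatment for each subject.
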